4.1.4. Handling of Missing and Incomplete Dates

In general, values for missing dates will not be handled unless methods for handling missing dates are specified in this section or relevant sections. The original reported dates collected on the eCRF should be used in all relevant listings. The following rules will be used for handling partial dates for analyses requiring dates.

Partial LP diagnosis date will be handled as follows:

- If only the day is missing, then the fifteenth of the month will be used.
- If both the month and day are missing, then 01 JUL of the year will be used.
- If the diagnosis date is completely missing, then the time since diagnosis will not be calculated.

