5.1. Inclusion Criteria

Participants are eligible to be included in the study only if all of the following criteria apply:

1. Ability to comprehend and willingness to sign a written ICF for the study.
2. Male or female aged 18 years or older.
3. Clinical diagnosis of LP with predominant cutaneous involvement.
4. IGA score of 3 or 4 at screening and baseline.
5. LP affecting $\leq 20\%$ of the BSA at screening and baseline.
6. Baseline LP-related Itch NRS score ≥ 4 . Baseline Itch NRS is defined as the 7-day average of Itch NRS score before Day 1 (data from a minimum of 4 out of 7 days directly prior to Day 1 is needed).
7. Willingness to avoid pregnancy or fathering children based on the criteria below.
 - a. Male participants with reproductive potential must agree to take appropriate precautions to avoid fathering children from screening through 90 days (a spermatogenesis cycle) after the last application of study treatment and must refrain from donating sperm during this period. Permitted methods in preventing pregnancy (see [Appendix A](#)) should be communicated to the participants and their understanding confirmed.
 - b. Female participants who are WOCBP must have a negative serum pregnancy test at screening and a negative urine pregnancy test before the first study cream application on Day 1 and must agree to take appropriate precautions to avoid pregnancy from screening through 30 days (1 menstrual cycle) after the last application of study treatment and must refrain from donating oocytes during this period. Permitted methods in preventing pregnancy (see [Appendix A](#)) should be communicated to the participants and their understanding confirmed.
 - c. A female participant not considered to be of childbearing potential as defined in [Appendix A](#) is eligible.

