6.1.3. Disease History

The time since disease duration will be summarized for all participants in the ITT population.

Time since diagnose (ie, disease duration [years]) will be calculated as follows:

$$\text{Disease duration (years)} = (\text{date of randomization} - \text{date of initial LP diagnosis} + 1) / 365.25.$$

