7.3.2. Subgroup Analyses for Primary Endpoint

Subgroups will be formed based on the following participant characteristics and baseline variables for those participants whose data are available:

- Sex: female versus male
- Baseline categorical age: ≥ 18 and < 65 versus ≥ 65
- Baseline duration of disease: ≤ 1 , > 1 and ≤ 5 , > 5
- Race: Black/African American versus White/Asian/other

The primary efficacy endpoint will be summarized using descriptive statistics based on the ITT population for the aforementioned subgroups.

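### The partial-date rule for LP diagnosis has no upper bound, so a partial date in the year or month of randomization can give a negative disease duration

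*SAP*

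**What the plan says.** SAP 4.1.4 gives three rules for an incomplete LP diagnosis date:

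- Day missing: "If only the day is missing, then the fifteenth of the month will be used".
- Month and day missing: "If both the month and day are missing, then 01 JUL of the year will be used".
- Nothing recorded: "If the diagnosis date is completely missing, then the time since diagnosis will not be calculated".

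SAP 6.1.3 introduces the derived variable with "Time since diagnose (ie, disease duration [years]) will be calculated as follows". The formula takes the randomization date minus the date of initial LP diagnosis, adds one day and divides by 365.25.

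The result is used in two places. It is summarized as a baseline characteristic (SAP 6.1.2 and 6.1.3), with mean and minimum among the statistics in SAP 5.1. It also defines a subgroup of the primary endpoint, "Baseline duration of disease" (SAP 7.3.2), with cut points at 1 and 5.

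**The concern.** Neither section limits the imputed date to a date on which the diagnosis could have been made, and neither sets a floor on the result. The instruction to query missing items in SAP 9.2.1 covers adverse events only. The eligibility criteria do not exclude the situation: Protocol 5.1 asks for "Clinical diagnosis of LP with predominant cutaneous involvement" and sets no minimum time since diagnosis. A participant may therefore enter in the same year, or the same month, as the diagnosis.

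For such a participant, a partial date can be completed to a day after randomization. The derived duration is then negative, which would mean that the participant was randomized before being diagnosed. One such value is enough to make the reported minimum negative. Correcting it during programming would depart from the SAP as written.

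**Working it through.** The plan states no duration that could be reproduced, so the check applies its formula to its imputed dates. The documents give no randomization dates. Every calendar day of 2023 and 2024 was tried, as an assumption.

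Formula (SAP 6.1.3): duration = (randomization date - diagnosis date + 1) / 365.25.

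**Year-only date, diagnosis in the year of randomization (imputed to 01 JUL)**

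| Randomized | Calculation | Years |
|---|---|---|
| 01 JAN 2023 | (-181 + 1)/365.25 | -0.493 |
| 01 JAN 2024 | (-182 + 1)/365.25 | -0.496 |
| 15 MAR 2023 | (-108 + 1)/365.25 | -0.293 |
| 29 JUN (either year) | (-2 + 1)/365.25 | -0.003 |
| 30 JUN (either year) | (-1 + 1)/365.25 | 0 |

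Every randomization date from 01 JAN to 29 JUN gives a negative value: 180 dates in 2023 and 181 in 2024.

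**Day-missing date, diagnosis in the month of randomization (imputed to the 15th)**

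| Randomized | Calculation | Years |
|---|---|---|
| 1st | (-14 + 1)/365.25 | -0.036 |
| 5th | (-10 + 1)/365.25 | -0.025 |
| 13th | (-2 + 1)/365.25 | -0.003 |
| 14th | (-1 + 1)/365.25 | 0 |

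The 1st to the 13th of each month are negative: 13 × 12 = 156 dates per year.

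**Subgroup.** A negative year-only value requires randomization by 29 JUN and a diagnosis no earlier than 01 JAN of that year. The longest possible true duration is then (179 + 1)/365.25 = 0.493 years in 2023 and (180 + 1)/365.25 = 0.496 in 2024. Both the negative value and the true value fall in the subgroup of at most 1, so no one is misclassified by this route.

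**Mean.** The number of affected participants is not given. As an illustration only, assume 0 to 3 of 60, each wrong by 0.5 years at most. The overall mean moves by 0 to 3 × 0.5/60 = 0.025 years, about 9 days. If all three were in one arm of 30, that arm's mean would move by 3 × 0.5/30 = 0.05 years.

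**With a cap at randomization.** The smallest duration is (0 + 1)/365.25 = 0.003 years. The participant randomized on 15 MAR 2023 with only the year recorded moves from -0.293 to 0.003. The true value for that person lies between 0.003 (diagnosed that day) and (73 + 1)/365.25 = 0.203 (diagnosed 01 JAN).

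**The case against.** The strongest objection is that the situation is rare and its extreme form hardly attainable. Take randomization on 08 JAN 2024 with only 2024 recorded: (-175 + 1)/365.25 = -0.476 years. Protocol 5.1 requires itch scores on at least 4 of the 7 days before Day 1, and Protocol 8.2.8.1 starts the diary on the day of screening. If randomization is on Day 1, screening was no later than about 04 JAN. A diagnosis made by then would date from 01 to 04 JAN, and under Protocol 8.1.5.2 the site records the diagnosis date at screening. A bare year for a diagnosis only days old is close to impossible. More generally, the most negative values need the narrowest diagnosis windows, in which the month is easiest to know. This objection stands, and it limits the size that can be claimed.

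It is also fair that fixed-date imputation always carries an error of up to about half a year, and that the cap does not recover the true date. What sets these cases apart is that the result is known to be impossible when it is computed.

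A reader might infer more than the documents support:

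- That recently diagnosed participants in general get negative durations. They do not; the diagnosis date must also be partial.
- That many such participants are to be expected because lesions mostly resolve over 1 to 2 years (Protocol 2.1). That describes how lesions resolve. Duration here runs from the initial diagnosis, and SAP 6.1.2 records the onset of the current episode separately.
- That future diagnosis dates would appear in the listings. SAP 4.1.4 keeps the originally reported dates there; only the derived duration is affected.

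**Conclusion.** The point holds as a small defect in a stated rule. SAP 4.1.4 and 6.1.3, applied as written, give a negative disease duration in exactly the two cases set out above. The mathematical limit is about -0.5 years for a year-only date and -0.036 years for a day-missing date; plausible values lie nearer zero. How often this happens cannot be told from the documents, and it may never happen.

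The consequence is confined to the descriptive summary of disease duration. The minimum could be impossible, and the mean would shift slightly under the assumed count. It would be wrong to read this as a threat to the efficacy results. The Cochran-Mantel-Haenszel test in SAP 7.3.1 is stratified by baseline IGA and does not use duration, and membership of the subgroup of at most 1 is unchanged.

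**What to change.** Add one sentence to SAP 4.1.4: after imputation, the LP diagnosis date is the earlier of the imputed date and the date of randomization. The smallest possible duration is then 1/365.25 years. In the affected cases the capped value is nearer the truth than a negative one, because the true duration cannot be below 1/365.25 years if diagnosis is on or before the day of randomization.

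The cost is that sentence and one line of code. No other analysis changes.

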4.2. Variable Definitions

4.2.1. Body Mass Index

Body mass index will be calculated as follows:

$$\text{Body mass index (kg/m}^2\text{)} = [\text{weight (kg)}] / [\text{height (m)}]^2$$

4.2.2. Prior and Concomitant Medication

Prior medication is defined as any nonstudy medication started before the first application of ruxolitinib 1.5% cream BID or vehicle cream BID.

Concomitant medication is defined as any nonstudy medication that is started accordingly:

- Before the date of first application of ruxolitinib 1.5% cream or vehicle cream and is ongoing throughout the study or ends on/after the date of first study drug application.
- On/after the date of first application of ruxolitinib 1.5% cream or vehicle cream and is ongoing or ends during the course of study.

A prior medication could also be classified as "both prior and concomitant medication" if the end date is on or after first application of ruxolitinib 1.5% cream or vehicle cream. In the listing, it will be indicated whether a medication is only prior, only concomitant, or both prior and concomitant.

For the purposes of analysis, all medications will be considered concomitant medications unless the medications can unequivocally be defined as not concomitant.

5. STATISTICAL METHODOLOGY

5.1. General Methodology

Unless otherwise noted, SAS® software (SAS Institute Inc, Cary, NC; v9.4 or later) will be used for the generation of all tables, graphs, and statistical analyses. Descriptive summaries for continuous variables will include, but not be limited to, the number of observations, mean, standard deviation, median, minimum, and maximum. Descriptive summaries for categorical variables will include the number and percentage of participants in each category.

5.2. Treatment Groups

This is a randomized, DBVC study followed by an OLE period. Table summaries, unless otherwise indicated, will present data by treatment group.

For the DBVC period, the treatment groups will be vehicle cream and ruxolitinib 1.5% cream.

For the OLE period, the participants will be grouped according to the treatment they received during the DBVC period:

- Vehicle cream to ruxolitinib 1.5% cream
- Ruxolitinib 1.5% cream

5.3. Analysis Populations

5.3.1. Intent-to-Treat Population

All participants who are randomized will constitute the ITT population. Treatment groups for this population will be defined according to the treatment assignment at the time of randomization regardless of the actual study drug the participant might take during their participation in the DBVC period.

The ITT population will be used for the summary of demographics, baseline characteristics, participant disposition, and analyses of all efficacy data.

5.3.2. Safety Population

The safety population will include all participants who applied ruxolitinib 1.5% cream BID or vehicle cream BID at least once. Treatment groups for this population will be determined according to the actual treatment the participant applied on Day 1 regardless of assigned study drug treatment.

All safety analyses will be conducted using the safety population.

5.3.3. Open-Label Extension Evaluable Population

All analyses for the OLE period will be conducted with the OLE evaluable population, which includes all participants who applied ruxolitinib 1.5% cream at least once during the OLE period.

6. BASELINE, EXPOSURE, AND DISPOSITION

[Appendix A](#) provides a list of planned tables, figures, and listings. Sample data displays are included in a separate document.

6.1. Demographics, Baseline Characteristics, and Disease History

6.1.1. Demographics and Baseline Characteristics

The following demographics and baseline characteristics will be summarized by treatment groups and overall for the ITT population in the DBVC period and for the OLE evaluable population in the OLE period: age, sex, race, ethnicity, weight, height, and body mass index.

6.1.2. Baseline Disease Characteristics and Disease History

For the ITT population, the baseline disease characteristics will be summarized by treatment group and will include, but not limited to, the following:

- Disease duration (years)
- LP diagnosis confirmed by previous biopsy (yes/no)
- Anatomic location (hands/wrists, forearms/arms, neck, face, ankle/feet, legs, back/buttocks, chest, abdomen, mucosal-mouth, mucosal-nose, mucosal-vulva/vagina, mucosal-esophagus, or other)
- Variant (type) of LP (hypertrophic LP, annular LP, bullous LP, actinic LP, LP pigmentosus, inverse LP, atrophic LP, lichen planopilaris [follicular LP], nail LP, mucosal LP-oral, mucosal LP-genital, mucosal LP-esophageal, mucosal LP-otic, indeterminate/unspecified, unknown, or other)
- Family history of LP (yes/no)
- History of skin infection related to LP requiring antibiotic treatment (yes/no)
- History of other skin diseases (yes/no)
- Days since onset of current episode of LP flare/activity
- Number of flares/episodes of LP in the past year other than current flare the participant experienced
- Clinical manifestations related to LP (% participants with each of the manifestations)
- Prior treatment received for LP (yes/no)

- Skin type using Fitzpatrick classification (Type I through VI)
- Total % BSA affected
- Baseline IGA score
- Baseline Itch NRS score
- Baseline Skin Pain NRS

6.1.3. Disease History

The time since disease duration will be summarized for all participants in the ITT population.

Time since diagnose (ie, disease duration [years]) will be calculated as follows:

$$\text{Disease duration (years)} = (\text{date of randomization} - \text{date of initial LP diagnosis} + 1) / 365.25.$$

6.1.4. Medical History

For participants in the ITT population during the DBVC period, medical history will be summarized by assigned treatment groups. This summary will include the number and percentage of participants with medical history for each body system/organ class as documented on the eCRF.

6.2. Disposition of Participant

The number and percentage of participants who were randomized, treated, and completed the DBVC period, as well as the number and percentage of participants who discontinued the treatment or withdrew from the study during the DBVC period with a primary reason for discontinuation, will be summarized as part of the ITT population.

The number and percentage of participants who completed the OLE period, in addition to those participants who discontinued treatment or withdrew from the study during the OLE period with a primary reason for discontinuation, will be summarized as part of the OLE evaluable population.

6.3. Protocol Deviations

Protocol deviations will be summarized and listed by treatment group and overall for ITT and OLE populations.

6.4. Exposure

For participants in the safety population in the DBVC period, the OLE evaluable population in the OLE period, and those who applied ruxolitinib 1.5% cream BID throughout the study, study drug exposure will be summarized by treatment group, descriptively, as follows:

- Duration of treatment (days):

Date of last application of ruxolitinib cream or vehicle cream in the specific period – date of first application of ruxolitinib cream or vehicle cream in the specific period + 1

- Total amount of cream applied (g):

Total weight of ruxolitinib cream or vehicle cream dispensed in the specific period – total weight of ruxolitinib cream or vehicle cream returned in the specific period

- Average daily application:

Total amount of cream applied in the specific period (g) / [duration of treatment with study cream in the specific period (days) – number of interrupted days with study cream in the specific period].

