6. STUDY TREATMENT

6.1. Study Treatments Administered

Ruxolitinib cream or matching vehicle will be applied as a thin film BID, with applications approximately 8 to 12 hours apart in the morning and in the evening at least 1 hour before bedtime.

At the baseline visit, an estimate of the %BSA to be treated will be used by the IRT system to calculate the number of tubes of study cream to be dispensed. During clinic visits, the participant should apply a thin film of study cream in front of site staff until all the affected areas to be treated are covered. This supervised application will be limited to 1 application of the study drug during the clinic visit. All areas identified at baseline should continue to be treated through the end of the DBVC period (Week 16) unless the participant meets criteria for stopping study cream. If there are new areas to be treated, including expansion of existing areas or development of new areas, after consultation with the investigator, study cream should be applied to these areas in addition to the areas treated at baseline (total affected areas \leq 20% BSA), and the percentage of BSA to be treated will be recalculated and increased. This new estimate will be entered into the IRT system to calculate the number of tubes of study cream to be dispensed. Participants whose new areas to be treated in addition to the areas identified at the baseline visit exceed 20% BSA should be discontinued from study treatment and the EOT assessment should be completed.

During the OLE period, starting at the Week 16 visit, the LP treatment areas will be evaluated by the investigator to assess if they still have disease and confirm whether the participant requires continuation of therapy (IGA score \geq 1) or can otherwise (re)enter the observation/no treatment cycle (IGA score = 0). Participants will stop treatment applications 3 days after all LP signs and symptoms have resolved. Multiple cycles of treatment/no treatment may be utilized as needed and treatment start/stop dates should be recorded by the participant in their eDiary. At any time during the OLE period, if a participant's new areas to be treated in addition to the areas identified at the previous visit exceed 20% BSA, then the participant should be discontinued from study treatment and the EOT assessment should be completed.

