The amount of study cream used per application will be determined by weighing a tube before and after the participant applies study drug to the affected areas. All tubes (including caps) of study cream will be weighed before being dispensed. All returned tubes (including caps) of study cream will also be weighed.

[Table 5](#) presents the study treatment information.

Table 5: Study Treatment Information

	Ruxolitinib	Vehicle
Mechanism of action:	JAK 1/2 inhibitor	Not applicable
Dosage formulation:	Cream	Cream
Treatment strength:	1.5%	Not applicable
Administration instructions:	DBVC period: Apply a thin film to affected areas identified at baseline in the morning and at least 1 hour before bedtime with applications approximately 8-12 hours apart for 16 weeks. OLE period: Apply a thin film to affected areas in the morning and at least 1 hour before bedtime with applications approximately 8-12 hours apart as needed for 16 weeks.	
Packaging and labeling:	Ruxolitinib or vehicle cream will be provided in 60-g tubes. Each tube will be labeled as required per country requirement.	
Storage:	15°C-30°C (59°F-86°F)	
Status of treatment in participating countries:	Investigational	

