6.5. Dose Modifications

There are no application adjustments/modifications allowed (decrease or increase in study drug frequency of application) except for study drug interruption or permanent discontinuation if needed (eg, for management of an AE).

Temporary interruption could be due to an AE during the DB VC or OLE period or clearance of the LP during the OLE period.

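### SAP 6.4 reports open-label no-treatment cycles that fall between two applications as days of treatment

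*SAP*

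**What the plan says.** SAP 6.4 (Exposure) gives one set of formulas for three summaries: the safety population in the double-blind period, the OLE evaluable population in the OLE, and participants on ruxolitinib throughout the study.

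- **Duration** is "Date of last application of ruxolitinib cream or vehicle cream in the specific period" less the matching first date, plus one day. Nothing else is subtracted.
- **Total amount** is "Total weight of ruxolitinib cream or vehicle cream dispensed in the specific period – total weight of ruxolitinib cream or vehicle cream returned" in the same period.
- **Average daily application** divides that amount by the duration less the "number of interrupted days with study cream in the specific period". The SAP does not define an interrupted day.

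Protocol 6.1 describes the OLE regimen: "Multiple cycles of treatment/no treatment may be utilized as needed and treatment start/stop dates should be recorded by the participant in their eDiary". Protocol 6.5 places clearance among the reasons for interruption: "Temporary interruption could be due to an AE during the DB VC or OLE period or clearance of the LP during the OLE period".

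On weighing, Protocol 6.1 states: "All tubes (including caps) of study cream will be weighed before being dispensed". Returned tubes are likewise weighed with their caps. SAP 6.4 has no rule for a tube that does not come back.

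**The concern.** A first-to-last date span is a fair measure of time on drug when application is continuous, as it is meant to be up to Week 16. The same formula is then applied to a period in which stopping on clearance and restarting on relapse is part of the design. A participant who clears, stops for some weeks and restarts has those weeks reported under the label of duration of treatment. The distortion falls on participants who clear and relapse.

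Protocol 2.1.1 gives long-term safety as one reason for having an OLE, so time on drug in that period is a figure readers will look for. The SAP offers no second figure that would show the time off cream: compliance in SAP 6.5 is computed for the double-blind period only. The average daily amount subtracts interrupted days, but without a definition a programmer could include or leave out clearance days.

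**Working it through.** The plan states no numeric exposure figure, so there is nothing to reproduce. The check applies the SAP 6.4 formulas to illustrative patterns.

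**Inputs from the documents.** OLE length is 16 weeks = 112 days, and total treatment is up to 32 weeks = 224 days (Protocol 4.2 and Table 2). Tube size is 60 g (Protocol Table 5). The formulas are from SAP 6.4.

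**Assumptions.** The lengths of the off-cream gaps, the use of 4 g/day while on cream, the tube counts and a packaging weight of 5 to 15 g per tube are all illustrative. The documents give none of them.

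**1. OLE duration, gap between two applications.** Reported duration = last date − first date + 1 = 112 days whatever the gap. Days on treatment = 112 − gap.

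| Days off between applications | Reported | On treatment | Excess |
|---|---|---|---|
| 14 | 112 | 98 | 112/98 − 1 = 14% |
| 28 | 112 | 84 | 112/84 − 1 = 33% |
| 56 | 112 | 56 | 112/56 − 1 = 100% |
| 84 | 112 | 28 | 112/28 − 1 = 300% |

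**2. Off-cream time at the end.** If the last 28 days are off cream, the last application is on day 84. Reported duration is 84 and days on treatment are 84, so there is no error.

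**3. Whole-study summary.** The mechanism is the same over a longer span. With 224 days and a 28-day gap, days on treatment are 224 − 28 = 196, and 224/196 − 1 = 14%. Here an off-cream stretch at the start of the OLE also lies between two applications, the last before Week 16 and the first after it, so it is counted too.

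**4. Average daily application.** At 4 g/day on cream and a 28-day gap, the total is 4 × 84 = 336 g. If clearance days are interrupted days, 336/(112 − 28) = 4.0 g/day, which is right. If they are not, 336/112 = 3.0 g/day, which is too low. With a 56-day gap the total is 4 × 56 = 224 g, and the two results are 224/56 = 4.0 and 224/112 = 2.0 g/day. The cycles therefore leave this measure correct or understate it.

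**5. Total grams.** Let t be packaging weight. Suppose 8 tubes are dispensed and 40 g is used from each returned tube, leaving 20 g.

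- All 8 returned: 8(60 + t) − 8(20 + t) = 320 g, the true amount. Packaging cancels.
- 7 returned, 1 not: 8(60 + t) − 7(20 + t) = 340 + t, or 345 to 355 g. True use is 340 g if the missing tube was emptied, 310 g if half used and 280 g if untouched. The excess runs from 5 g (5/340 = 1.5%) to 75 g (75/280 = 26.8%).

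**The case against.** The strongest reply is that the elapsed span is a legitimate quantity. The treatment-emergent window in SAP 9.2.1 runs from first application to 30 days after the last in the period, off-cycles included, so the span tracks the time over which events are counted. This stands as a reason to keep the span. It does not justify calling it duration of treatment with no days-on-treatment figure beside it.

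Three stronger readings are tempting, and the documents do not support them.

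- **That all reported exposure is overstated.** Off-cream time after the last application is excluded. Participants who apply no cream in the OLE are outside the OLE evaluable population (SAP 5.3.3). The average daily amount is never inflated by the cycles.
- **That the safety results are made to look better.** SAP 9.2.2 plans numbers and percentages of participants with events. No rate per day or per gram is specified in the available text, so no planned safety statistic there uses duration or grams as its denominator.
- **That unreturned tubes materially inflate grams.** Packaging cancels for every returned tube. Participants are told to bring all cream to visits (Protocol 6.4), and sites collect all used and unused containers (Protocol 6.2). Some non-return is foreseeable, since Protocol 7.3 provides for loss to follow-up, but neither a non-return rate nor a packaging weight is given. Entering such a tube at full weight is what the formula yields when the returned weight is zero. It is not a rule the SAP states.

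**Conclusion.** The point holds for duration. Followed literally, SAP 6.4 reports no-treatment cycles between two applications as days of treatment, in the OLE and in the whole-study summary for those on ruxolitinib throughout. The excess depends on the gap, from 14% for 14 days off to 300% for 84 days off in a 112-day span. The last is a constructed extreme, with cream used on only 28 of 112 days. How many participants will clear and relapse is not given, so the effect on group summaries cannot be stated.

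The lack of a definition of interrupted days is a smaller gap in the same section. Protocol 6.5 points to the reading that gives the correct average.

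The unreturned-tube point is secondary and conditional. It is real for each tube affected, but its overall size cannot be determined from the documents.

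Exposure is summarized descriptively. The primary test, the double-blind efficacy comparison and the planned adverse event percentages are unchanged.

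**What to change.** In SAP 6.4, for the OLE and whole-study summaries:

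1. Report days on treatment as the sum of days within treatment cycles, from the eDiary start/stop dates collected under Protocol 6.1. State how a missing stop date is handled.
2. Show the first-to-last span separately, labelled elapsed duration.
3. State that clearance-related no-treatment days count as interrupted days in the average daily application, consistent with Protocol 6.5. Keep the elapsed span as the starting point of that denominator. If days on treatment were put there instead, clearance days would be subtracted twice.
4. For total grams, report how many tubes were not returned and how many participants this affects. Show grams with and without the intervals concerned. Both versions are needed, because leaving those intervals out tends to remove participants lost to follow-up, which is itself selective in a trial of about 60.

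The cost is SAP text, programming and a few extra table rows. No new data are needed, though the days-on-treatment figure will be only as complete as the eDiary cycle dates.
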